**Emory University Investigator**

[name], Assistant Professor of Medicine, Department of Cardiology

**Introduction/Background:** Catheter ablation of cardiac arrhythmia is performed to offer symptomatic relief from a variety of atrial, ventricular and atrio-ventricular rhythms. Irrigated ablation catheters are commonly used for ablation of arrhythmias arising from the left heart and coronary sinus, to mitigate potentials risks of catheter ablation, including char formation on the catheter tip. These catheters contain internal channels allowing for infusion of an external fluid directly to the tip of the catheter, where the fluid is sprayed through numerous end holes allowing for cooling of the catheter ablation tip. Normal and half normal saline are the most commonly used irrigant fluids.

Fluid filled catheters are also the primary tool utilized to assess intravascular and intracardiac pressures and hemodynamics in the cardiac catheterization suite and intensive care unit. Intravascular hemodynamics allow assessment and diagnosis of a variety of cardiac conditions which are commonly found in patient undergoing catheter ablation, including congestive heart failure, diastolic dysfunction, and valvular heart disease. However, the fluid filled catheters commonly used for these assessments are single lumen and generally have a minimal diameter of 5 French for intracardiac catheters. Principles of fluid mechanics are characterized by Poiseuille's law and Bernoulli's law, which suggest that the radius of the fluid filled catheter will impact the reliability of the reading. "Dampening" of pressure waveforms are observed in smaller diameter catheters and may lead to underestimation of peak pressure and overestimation of the nadir pressure gradient.

It is unknown if transduction of pressures from the tip of an irrigated ablation catheter will yield equivalent results compared to use of a single 5F lumen catheter.

The purpose of this study is to test the hypothesis that transduction of intracardiac pressures using an irrigated ablation catheter placed as standard of care for the ablation procedure is equivalent to transduction of pressures using a standard 5F balloon tipped PA catheter placed only for this research study.

### **Objectives:**

The main objective of this study is to take intracardiac pressure measurements and pressure waveforms with both a "gold standard" balloon tipped pulmonary artery catheter placed for this study and an irrigated ablation catheter placed as standard of care for the procedure in order to evaluate the following 2 questions:

1. Determine accuracy of intracardiac pressure measurements as assessed by the balloon tipped pulmonary artery catheter and by an irrigated ablation catheter.
2. Determine accuracy of intracardiac pressure waveforms measured by the balloon tipped pulmonary artery catheter and by an irrigated ablation catheter.

**Research Design:** The study will occur in patients undergoing routine cardiac ablation of his/her arrhythmia with planned use of an irrigated ablation catheter. The irrigation port of the irrigated ablation catheter will be connected via a three way stop cock to the irrigation tubing via 1 port and to a pressure transducer via the second port (see figure 1). All ports will be flushed through to the tip of the catheter to ensure no air in the line, per standard protocol. The pressure transducer will be leveled and “zeroed” per routine using CARDIOLAB software. A 5F MPA catheter will be prepared in similar fashion to the ablation, without an irrigant line running. “Zero” will be confirmed by positioning each catheter next to each other and assessing for equal waveform values.

Ablation and catheter manipulation will be done per routine under the supervision of a qualified electrophysiologist. The pressure line will be left “off” with the stopcock during the EP study and ablation, and whenever pressure assessment is not being performed.

After completion of ablation/study, the ablation catheter will be serially positioned in the cardiac chambers (left OR right atrium, left OR right ventricle). Because pressure values, slopes and characteristics are similar between the atria and ventricles, all 4 chambers will not be sampled. The stop cock will be turned to the pressure transducer and waveforms will be stored corresponding to each chamber. Next, the catheter will be removed and replaced with a 5F balloon tipped PA catheter which will be positioned under fluoroscopic guidance in each previously evaluated chamber. The placement of the balloon tipped PA catheter and measurements for this study will take about 10 additional minutes.

Figure 1: Stop cock connected to irrigant port of ablation catheter. In current position, standard irrigant is flowing through catheter via manufacturer pump.

[figure not shown]

Figure 2: Stop cock is now turned to open the irrigant port to the pressure sensing line. In this configuration, pressure is transduced from the tip of the catheter.

**Risks/benefits:** Risks of this procedure are related to insertion of the balloon tipped pulmonary catheter into the heart. The catheter will be placed through access sites in the right and left femoral vein which are used for the ablation (no new vein access is required for this study)

Insertion risks include <1% risk of stroke, infection, damage to heart or valves or damage to conduction centers of heart.

Potential benefits to the subject include assessment and analysis of intracardiac pressures by the 'gold-standard' technique which can be useful in diagnosing conditions such as congestive heart failure, valve disease and diseases of the pericardium. Some patients develop shortness of breath after ablation procedures, and this can be prevented with assessment of intracardiac pressures after ablation. Although the purpose of this study is to assess the accuracy of these measurements from the ablation catheter, any unexpectedly abnormal patient findings such as elevated pressures or evidence of valve disease will be evaluated further per standard practice (echo, overnight observation, administering diuretic medications).

Potential benefits not to the subject include improved safety and monitoring during ablation procedures for future patients undergoing ablation.

**Data to be collected:** The patients' demographics, ablation indication, and prior echocardiogram study (when available) will be retrieved from chart review. The systolic, diastolic, and mean pressure values and waveform tracings for each heart chamber assessed will be collected during the procedure.

**Data Storage:** Data will be stored on Emory HIPAA compliant servers. All documents and information will be password protected with no information saved to personal computers.

**Patient selection:** Study patients will be recruited among all patients older than 18 years old undergoing elective ablation for an arrhythmia at Emory University Hospital. Up to 15 patients will be enrolled in order to obtain a minimum of 10 useable comparison datasets.

**Informed Consent:** Following education on the study protocol, patients will be offered the option to enroll. Informed consent will be obtained by approved research personnel in a private area. If the patient agrees to participate, consent will be documented. Consent will occur the day of the scheduled ablation procedure.

**Compensation for time and effort:** There is no compensation for participation in this study. This research will add about 10 minutes to the standard of care procedure. .

**Data analysis:** The systolic, diastolic and mean pressure values for each chamber assessed will be compared between the RF ablation catheter derived measurement and the MPA catheter measurement. Measurements will be made in duplicate for each value. Comparison will be made using T – Test and a Kappa statistic.

Waveforms will be compared using a MACLAB system, by determining a mean gradient between the two waveforms. These values will be compared using a T –Test. All analyses will be performed using Microsoft Excel and Graphpad Prism.

**Safety:** Positioning of both catheters (ablation catheter and PA catheter ) will be done under continuous ultrasound guidance to ensure positioning of the catheter without secondary damage to the heart, heart valves or heart muscle. Fluoroscopy and 3-dimensional computer mapping will be used or immediately available for use in assisting positioning when needed. All catheter manipulation will be done by an experienced, Board certified cardiologist with greater than 10 years of experience in PA catheter manipulation and positioning [name].

The tip of the PA catheter has a balloon which will be inflated whenever advancing the balloon forward. This reduces risk of perforation as the catheter will bounce off the walls of the heart when encountered.

The catheter will be primarily position with use of guiding catheters which are already position in the chamber of interest(s) for the purpose of the catheter ablation procedure itself. This will also help minimize risk and time associated with PA catheter manipulation.

Equipment necessary to treat potential complications of catheter manipulation such as fluid or bleeding around the heart will be immediately available in the procedure suite. Operators will be experienced and qualified to perform stabilizing and treating procedures in case of such emergency.

**Safety analysis:** Safety assessments will consist of monitoring and recording all adverse events and serious adverse events. While they are not anticipated, adverse events will be summarized using the frequency of subjects for each level.

**Data and Safety Monitoring Plan:** Oversight of the progress and safety of the trial will be provided by the PI. Adverse events are not anticipated, but any occurring will be reported to Emory IRB policies and procedures.

Monitoring will be conducted on-site as self-monitoring using the Emory IRB (CTAC) self-monitoring tool. Self-monitoring will occur after the first subject is enrolled and will also occur after 5, 10, and 15 subjects (study completion) have been enrolled. As stated the CTAC self-monitoring tool will be followed, with special emphasis on examining procedural safety

associated with the PA catheter manipulation and ensuring compliance with the measurement technique as stated in the protocol. Any reportable safety event or reportable protocol deviation will be promptly reported to the Emory IRB.

**Confidentiality:** Patients will be assigned an identifier number. Data will be stored on a secure drive supported by Emory healthcare. Only pertinent members of Emory Healthcare/ SOM who have undergone HIPAA training will have access to the spreadsheet. PHI information including the informed consent forms will be stored in a locked space in the PI's office.

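### The objectives promise accuracy, but two catheters compared only with each other, without an independent standard, can yield only the difference between them

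*Combined protocol and SAP*

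**What the plan says.** The Objectives section gives two aims. The first is "Determine accuracy of intracardiac pressure measurements as assessed by the balloon tipped pulmonary artery catheter and by an irrigated ablation catheter"; the second is "Determine accuracy of intracardiac pressure waveforms measured by the balloon tipped pulmonary artery catheter and by an irrigated ablation catheter". Both apply the word accuracy to both catheters. Risks/benefits repeats the aim for one of them: "the purpose of this study is to assess the accuracy of these measurements from the ablation catheter".

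The measurements come from a "balloon tipped pulmonary artery catheter placed for this study and an irrigated ablation catheter placed as standard of care for the procedure", and the first of these is labelled the gold standard. No third measurement, external pressure standard or dynamic-response test of either catheter is described. Under Research Design, the transducer is levelled and zeroed in the routine way, and the zero is then confirmed by placing the catheters side by side and looking for equal values. Under Data analysis, pressure values are compared between the catheters by t-test and kappa, and waveforms by the mean gradient between the two tracings.

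The Introduction states a different aim. The hypothesis is that transduction through the irrigated catheter "is equivalent to transduction of pressures using a standard 5F balloon tipped PA catheter placed only for this research study". No equivalence margin is given.

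The comparator is named in three ways: a single 5F lumen catheter (the open question in the Introduction), a 5F MPA catheter (Research Design, shortened to MPA catheter in Data analysis), and a 5F balloon tipped PA catheter (the hypothesis and Research Design).

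**The concern.** Accuracy is closeness to the true pressure. Estimating it needs the truth, or a standard whose own error is known to be negligible or has been measured. Here each catheter is judged only by the other. Read literally, the objectives also ask for the accuracy of the PA catheter, which would have to be its own yardstick.

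What is at stake is the conclusion. If the two catheters agree, the study could report the ablation catheter as accurate when the data show only that it reads like the PA catheter. Risks/benefits anticipates better monitoring of future ablation patients, so readers may take the word at face value. If the catheters differ, the data alone cannot say which one is off.

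Reference error is not a remote idea in this protocol. The Introduction says that fluid-mechanical principles "suggest that the radius of the fluid filled catheter will impact the reliability of the reading", a statement about fluid-filled catheters in general.

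**Working it through.** **The plan's own figure.** The only sample-size statement is up to 15 enrolled for at least 10 usable datasets. This is consistent with 10 / (1 − 1/3) = 15. The one-third loss is implied, not stated. No alpha, power, SD, effect size or margin is given, so there is no power or precision calculation to reproduce.

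**What the data can identify.** Let T be the true pressure, A = T + bA + e1 the ablation-catheter reading and R = T + bR + e2 the PA-catheter reading, where bA and bR are the biases. Then

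mean(A − R) estimates bA − bR.

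T cancels, and neither bA nor bR can be recovered alone. The readings are in fact sequential. Any change in T between them adds to the difference and does not help to separate the biases. Duplicate readings inform repeatability (the spread of e1 and e2), not bias. Routine zeroing sets a static baseline, and the side-by-side check is again a comparison of one catheter with the other.

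**Simulation.** 20,000 replicates, n = 10 pairs, two-sided paired t-test at 0.05. Assumptions, none from the documents: T has mean 120 and SD 20 mmHg, random error SD is 3 mmHg per catheter, and biases are as listed. The plan does not say that its t-test is paired; pairing is assumed.

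| True error of ablation catheter (mmHg) | True error of PA catheter (mmHg) | Mean A − R (mmHg) | t-test rejects |
|---|---|---|---|
| 0 | 0 | 0.0 | 5.2% |
| −5 | −5 | 0.0 | 5.0% |
| −10 | −10 | 0.0 | 5.0% |
| −5 | 0 | −5.0 | 91% |
| 0 | +5 | −5.0 | 91% |
| −10 | −5 | −5.0 | 91% |

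The first three rows cannot be told apart by the study, and neither can the last three. The mmHg values illustrate this; they do not estimate what will happen.

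**Why the planned tests do not show agreement either.** With S the SD of the paired differences, the 95% half-widths are:

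- Mean difference, t/√n: n = 10 gives 2.262/√10 = 0.72 S; n = 15 gives 2.145/√15 = 0.55 S.
- Each limit of agreement, t·√(1/n + 1.96²/(2(n − 1))): n = 10 gives 1.27 S; n = 15 gives 0.97 S.
- True mean difference detected with 80% power: 1.00 S at n = 10; 0.78 S at n = 15.

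Under the simulation's assumptions S = √(3² + 3²) = 4.24 mmHg, so at n = 10 the mean difference is known to about ±3.0 mmHg (0.715 × 4.24). A non-significant t-test is therefore compatible with a real difference, and no margin is stated against which to call it small. Kappa needs categories, and none is defined for pressures recorded on a continuous scale.

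**The case against.** The best reply is that accuracy here means accuracy relative to the accepted clinical reference. The protocol labels the PA catheter the gold standard and frames its hypothesis as equivalence to it. That is a fair reading, and it keeps this point from undermining the comparison. But the Introduction and the Objectives then state different aims, and only the Introduction's aim matches the data. The reply does not rescue the accuracy of the PA catheter itself, which both objectives name.

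Several stronger readings are tempting and are not supported:

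- *That the protocol says its own reference is damped.* The Introduction attributes damping to catheters of smaller diameter, just after giving 5F as the usual minimum for intracardiac pressure catheters, and then poses the open question that begins "It is unknown if transduction of pressures from the tip of an irrigated ablation catheter will yield equivalent results compared to use of a single" and ends by naming the comparator. In context 5F is the benchmark, and the doubt falls on the irrigated catheter. Damping of the reference can be inferred from the general remark about radius, but the protocol does not state it.
- *That the balloon makes the reference's pressure channel narrower.* The Safety section says only "The tip of the PA catheter has a balloon which will be inflated whenever advancing the balloon forward". No lumen size or construction is given.
- *That a specific mmHg error is being hidden.* Any such figure needs assumed lumen sizes, damping and pressures. Loss of swing about the mean would also leave mean pressure, one of the three recorded values, unaffected.
- *That the analysis scores the PA catheter as truth.* The t-test and the mean gradient are contrasts between the catheters. Neither regresses on the reference nor marks one catheter as wrong.
- *That the plan as written at least shows agreement.* It does not, for want of a margin and limits of agreement.

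**Conclusion.** The point holds as a mismatch between claim and design. The data can estimate the difference between the irrigated ablation catheter and the 5F PA catheter. They cannot give the accuracy of either, and error shared by both cannot be detected. This follows from having two methods and no independent standard; it does not depend on the simulated values or on whether the reference is damped.

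The size of any shared error cannot be derived from the documents. The comparison itself remains valid and worth making. What should change is the wording of the objectives, the scope of the conclusion, and an analysis that cannot at present support agreement or equivalence. The change should be made before the data are analysed.

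**What to change.** 1. **Objectives and Risks/benefits.** Replace accuracy in both objectives and in the Risks/benefits sentence with agreement with, or equivalence to, the 5F balloon-tipped PA catheter, as in the Introduction's hypothesis. Limit the study conclusion to that catheter and state that error common to both catheters cannot be detected. The gold-standard label may stay as a name for the comparator, provided it is not offered as something the study establishes.
2. **Data analysis.** For each pressure value and chamber, report the mean paired difference with its 95% confidence interval and the limits of agreement with theirs, plotted against the average of the two catheters. Judge them against a margin that the investigators set and justify before analysis. State how duplicates enter, because limits computed from averaged duplicates are narrower than those for single readings. Drop kappa unless categories are defined in advance, and do not read a non-significant t-test as agreement.
3. **Comparator.** Use one name and description throughout, reconciling the single 5F lumen, 5F MPA and 5F balloon-tipped PA wordings.

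Cost: text changes in a few sections, a little more analysis, and a slightly less favourable claim. No extra patients or measurements are needed. If absolute accuracy is truly intended, rewording will not be enough and an independent pressure standard would be required.

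### Does measuring only the left or right atrium and ventricle in each patient, on an unsupported similarity statement, undermine the catheter comparison?

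*Combined protocol and SAP*

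**What the plan says.** The Introduction/Background gives the study's purpose as follows: "test the hypothesis that transduction of intracardiac pressures using an irrigated ablation catheter placed as standard of care for the ablation procedure is equivalent", the comparator being the reference catheter. It names no chamber.

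Under Research Design, once the ablation is complete, "the ablation catheter will be serially positioned in the cardiac chambers (left OR right atrium, left OR right ventricle"). The reason given for not visiting every chamber is: "Because pressure values, slopes and characteristics are similar between the atria and ventricles, all 4 chambers will not be sampled". The reference catheter then goes to the chambers already measured. No rule for choosing the side is stated.

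On the unit of data, Research Design says "waveforms will be stored corresponding to each chamber", and Data to be collected says "waveform tracings for each heart chamber assessed will be collected during the procedure", together with systolic, diastolic and mean values. Data analysis compares those three pressures between catheters chamber by chamber. Its waveform comparison, a mean gradient between the two tracings, mentions no chamber.

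On numbers, Patient selection says "Up to 15 patients will be enrolled in order to obtain a minimum of 10 useable comparison datasets". No minimum is set by side or chamber.

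**The concern.** Three features together look like a weakness.

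- **The similarity statement is bare and loosely worded.** Taken literally it says that atria resemble ventricles. The left-or-right design needs a different claim, that left resembles right within each chamber type. Neither is supported by data, and a reader may doubt the second for the ventricles.
- **The hypothesis is broader than the sampling.** The plan could end with a statement about intracardiac pressures in general when one side has few or no paired readings. The Introduction/Background makes an uneven split plausible: "Irrigated ablation catheters are commonly used for ablation of arrhythmias arising from the left heart and coronary sinus".
- **Merging is not ruled out.** An analyst who relied on the similarity statement might combine left and right. The Introduction/Background warns that damping in narrower catheters "may lead to underestimation of peak pressure and overestimation of the nadir pressure gradient". If that error grew with pressure amplitude, a combined ventricular mean would depend on the mix of sides enrolled.

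At stake would be a mean difference that describes neither side, and a claim reaching beyond the data.

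**Working it through.** The plan states no figure on this point that could be reproduced. The check takes the logic first, then the size.

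**1. What the similarity statement means.** The text just before it lists an atrium and a ventricle, each left or right. If atria were being called similar to ventricles, measuring both would serve no purpose. Only left similar to right explains the design, so context settles the reading.

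**2. Whether the comparison needs the statement to be true.** For a given patient and chamber, the difference is d = (ablation catheter reading) − (reference catheter reading). Both readings come from the same chamber, so d needs no assumption about any other chamber. Similarity matters only for merging sides or for extending the result to chambers not measured.

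**3. What the plan does with d.**

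| Section | Unit |
|---|---|
| Research Design | waveforms stored by chamber |
| Data to be collected | values and tracings by chamber assessed |
| Data analysis, pressures | compared by chamber assessed |
| Data analysis, waveforms | not stated, but each gradient comes from tracings stored by chamber |

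No section proposes merging left and right.

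**4. What merging would do.** Let the mean error be b_L on the left and b_R on the right, with left share q. The merged mean estimates q·b_L + (1 − q)·b_R, which depends on q only if b_L ≠ b_R. Estimates by chamber target b_L and b_R whatever q is. The documents give no value for b_L, b_R or q.

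**5. How sparse a side could be.** Assume one dataset per patient, independent patients, and X ~ Binomial(n, q) left-sided for one chamber type. The shares 50%, 70% and 80% are assumptions. Patient selection gives n = 10 as the minimum of usable datasets; 15 is maximum enrolment, so 15 usable is the best case.

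| | q = 0.5 | q = 0.7 | q = 0.8 |
|---|---|---|---|
| n = 10, smaller side ≤ 2 | 10.9% | 38.4% | 67.8% |
| n = 15, smaller side ≤ 2 | 0.7% | 12.7% | 39.8% |
| n = 10, one side empty | 0.2% | 2.8% | 10.7% |
| n = 15, one side empty | <0.1% | 0.5% | 3.5% |

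For example, at n = 10 and q = 0.5 the first entry is 2 × (1 + 10 + 45)/1024 = 112/1024 = 10.9%. The chance of an empty side is q^n + (1 − q)^n, which at n = 10 and q = 0.8 is 0.107 plus a negligible term.

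**6. Precision by chamber.** With one difference per patient, the 95% confidence half-width in SD units of the paired difference is t(0.975, n − 1)/√n.

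| n | 15 | 10 | 5 | 3 | 2 |
|---|---|---|---|---|---|
| half-width (SD) | 0.55 | 0.72 | 1.24 | 2.48 | 8.98 |

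At n = 10 this is 2.262/3.162 = 0.72. An even split of 10 leaves 5 per side, and 2.776/2.236 = 1.24. These widths show the cost of dividing any small sample; they do not measure an error caused by the sampling rule.

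**The case for a change.** The best case for a change is that it would be nearly free. Data are already held by chamber, so a few sentences in Data analysis could name the four chambers as strata, cover the waveform gradients, and confine the conclusion to what was measured. The unsupported statement invites an atrium-versus-ventricle grouping, the hypothesis carries no chamber limit, and the waveform sentence names no unit.

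Part of this stands. The statement is unsupported, the strata are not spelled out, and a sparse side is quite possible. None of it shows that the analysis as written goes wrong. An analyst following Data analysis would compare pressures within each chamber, and would handle gradients from chamber-specific tracings in the same way. Confining the conclusion to the chambers measured is ordinary reporting practice. A flat ban on merging would also be open to debate: a pooled model with a chamber term and allowance for within-patient correlation is a reasonable alternative, and four separate estimates from 10 to 15 patients may leave one with only two observations.

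The sampling also has a practical rationale, though the plan does not offer it as one. The Safety section says the reference catheter is placed mainly through guiding catheters already in position for the ablation, to limit risk and handling time. The study needs no new venous access and adds roughly ten minutes. Sampling every chamber would press against those limits.

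**Conclusion.** No change to the plan is needed. The similarity statement is loose and unsupported, but the paired comparison does not rest on it, and the by-chamber wording already points to the right analysis. Harm would require three things together: a merge of sides that the plan does not propose, a catheter error that differs by side (not shown in the documents), and a report that generalises beyond the chambers measured.

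The chance of a sparse side could be considerable, 11% to 68% for 2 or fewer patients with 10 datasets. That range rests on assumed left shares of 50% to 80% and one dataset per patient. It describes imprecision, which the number of patients and the confidence interval in each chamber would show; it does not describe bias. Writing down the strata would record what a careful analyst would do anyway, with little or no effect on the result. The plan also sets no equivalence margin. That is a separate and weightier matter, and intervals by chamber would not resolve it.

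### Does the plan need to report how often the ablation catheter fails to give a readable pressure trace?

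*Combined protocol and SAP*

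**What the plan says.** Patient selection sets the numbers: "Up to 15 patients will be enrolled in order to obtain a minimum of 10 useable comparison datasets". The word useable is not explained, and the protocol does not say whether a dataset is counted per patient or per chamber. Under Research Design each patient is measured in one atrium and one ventricle, first with the ablation catheter and then with the balloon-tipped catheter.

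For the procedure itself, Data to be collected lists pressures and tracings only: "The systolic, diastolic, and mean pressure values and waveform tracings for each heart chamber assessed will be collected during the procedure". Data analysis then says: "Comparison will be made using T – Test and a Kappa statistic". Waveforms are compared through the mean gradient between the two traces. The t-test is not said to be paired, but kappa and the gradient each need a reading from both catheters.

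The Objectives section names two questions, the accuracy of the pressure values and the accuracy of the waveforms. Success in obtaining a trace is not among them. The Data and Safety Monitoring Plan provides for self-monitoring of safety and of compliance with the measurement technique, and it treats 15 enrolled subjects as the end of the study.

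**The concern.** The Introduction frames the question as an open one: "It is unknown if transduction of pressures from the tip of an irrigated ablation catheter will yield equivalent results". Risks/benefits gives the hoped-for use: "Potential benefits not to the subject include improved safety and monitoring during ablation procedures for future patients undergoing ablation". For monitoring, a method that agrees well when it works but often gives no trace is worth less than one that nearly always works.

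The planned results describe agreement where both catheters gave a reading. If enrolment continued only until ten such datasets existed, the same ten pairs could come from ten attempts without failure or from fifteen attempts with five failures, and no planned result would tell these apart. The number enrolled less the number analysed would help only in part. It mixes ablation-catheter failures with failures of the reference catheter and with procedures not completed after consent ("Consent will occur the day of the scheduled ablation procedure"). It could also hide a failure confined to one chamber.

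**Working it through.** **Inputs.** A maximum of 15 enrolled and a minimum of 10 useable datasets (Patient selection). The documents give no failure rate. Below, *f* is an assumed per-patient probability of no ablation-catheter trace, independent between patients, and 10% is an assumed loss from other causes.

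**1. What the allowance covers.** (15 − 10)/15 = 5/15 = 33%. Conversely, 10/(1 − 1/3) = 15. The documents give no loss rate from which 15 was derived, so this is only the implied maximum.

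**2. Chance of reaching ten pairs from 15 attempted patients.** P(X ≥ 10), with X ~ Binomial(15, 1 − *f*), or Binomial(15, 0.9(1 − *f*)) when the other losses are added:

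| *f* | ablation-catheter failure only | plus 10% other loss |
|---|---|---|
| 10% | 0.998 | 0.951 |
| 20% | 0.939 | 0.778 |
| 25% | 0.852 | 0.645 |
| 1/3 | 0.618 | 0.403 |

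A failure rate near one in five could pass without the study missing its minimum. At one in four with other losses, the chance of falling short is 1 − 0.645 = 0.355, and a shortfall would be plain to any reader.

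**3. Effect on the planned agreement results.** The mean difference is the sum of the observed differences divided by the number of pairs, and the SD uses the same differences. An attempt with no ablation-catheter reading adds nothing to either the sum or the count. It reduces the number of pairs and therefore the precision; it does not shift the estimate of agreement where both readings exist. Bias needs something else: readable pairs set aside because the two values disagree. The documents neither state nor exclude this.

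**4. Does the same ten pairs hide different failure counts?** Exact (Clopper-Pearson) 95% intervals for the failure proportion:

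| failures/attempts | proportion | 95% interval |
|---|---|---|
| 0/10 | 0% | 0 to 31% |
| 2/12 | 17% | 2 to 48% |
| 5/15 | 33% | 12 to 62% |

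This contrast requires enrolment to stop at the tenth pair. The protocol has no such rule and no replacement rule. If 15 patients are enrolled and attempted, with no other losses, 2 failures leave 15 − 2 = 13 pairs and 5 failures leave 10, so the number analysed itself shows the difference.

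**5. What a reported rate would be worth.** With no failure in 15, the upper limit is 1 − 0.025^(1/15) = 0.218. With 3 failures in 15 (20%), the interval is 4% to 48%. The best possible outcome still admits a failure rate above one in five.

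**The case for a change.** The strongest case for a change is that the failure is foreseeable and the remedy costs little. The Introduction itself warns that small lumens damp the waveform, so poor traces from the ablation catheter are a likely way for the method to fall short. An undefined criterion of usefulness leaves room, at least in principle, for someone to discard a damped but readable trace after seeing how far it lies from the reference. A definition fixed beforehand and one log line per catheter and chamber would close that door without extra patients or measurements, and reasons not written down during the procedure may be difficult to recover.

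Part of this stands. The term is undefined, the unit of counting is unstated, and no log of reasons is planned. The rest is weaker. The protocol predicts damping, meaning peaks read too low and troughs too high, rather than absence of a trace. A damped trace is readable and belongs in the comparison, and nothing in the text directs anyone to remove it. Recovery is also easier than the objection suggests: waveforms are stored for each chamber with the stopcock open to the transducer, no wording restricts storage to good ones, and a flat or poor tracing could be counted later. The catheters are also placed side by side beforehand to check that their readings match, which should expose a line that does not transmit. A rate of obtained traces, split by chamber and catheter, would mean four proportions on at most 15 patients each, for a question the protocol does not ask.

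**Conclusion.** The observation is correct but does not call for a change. Followed as written, the plan gives no wrong answer on accuracy because of this point. The count of failed traces lies outside both objectives, and at 15 patients it could only be descriptive (0 of 15 still allows 22%).

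Analysts can fill the gap in the ordinary way. A dataset is useable when both catheters gave readable values in the chamber concerned. Readable traces stay in, damped or not. The report states how many patients were enrolled and analysed, and why any were left out.

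This conclusion rests on one assumption that the text neither confirms nor contradicts: that no readable pair is excluded because its two values disagree. The completion probabilities (94% at an assumed one-in-five failure rate, 78% with an assumed 10% further loss) also assume independent patients and 15 attempts. They show that moderate failure could go without a planned count, not that it is expected.
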